8.2.4 Expectedness

Adverse Events can be Expected or Unexpected.

An expected adverse event is an event previously known or anticipated to result from participation in the research study or any underlying disease, disorder, or condition of the subject. The event is usually listed in the Investigator Brochure, consent form or research protocol.

An unexpected adverse event is an adverse event not previously known or anticipated to result from the research study or any underlying disease, disorder, or condition of the subject.

8.2.5 Attribution

Attribution is the relationship between an adverse event or serious adverse event and the study drug. Attribution will be assigned as follows:

- Definite – The AE is clearly related to the study drug.
- Probable – The AE is likely related to the study drug.
- Possible – The AE may be related to the study drug.
- Unlikely – The AE is doubtfully related to the study drug.
- Unrelated – The AE is clearly NOT related to the study drug.

8.3 Reporting Procedures for All Adverse Events

All participating investigators will assess the occurrence of AEs throughout the subject's participation in the study. The clinical course of each event will be followed until resolution, stabilization, or until it has been determined that the study treatment or participation is not the cause.

The investigator is responsible for ensuring that all adverse events observed by the investigator or reported by the subject which occur after the subject has signed the informed consent are fully recorded in the subject's case report form, subject's medical records, and/or any other institutional requirement. Source documentation must be available to support all adverse events.

A laboratory test abnormality considered clinically relevant (e.g., causing the subject to withdraw from the study), requiring treatment or causing apparent clinical manifestations, or judged relevant by the investigator, should be reported as an adverse event.

The investigator will provide the following for all adverse events:

- Description of the event
- Date of onset and resolution
- Grade of toxicity
- Attribution of relatedness to the investigational agent
- Action taken as a result of the event
- Outcome of event

In this study, descriptions and grading scales found in the NCI Common Terminology Criteria for Adverse Events (CTCAE) version 4.0 available at <http://ctep.cancer.gov> will be utilized for AE reporting.

Investigative sites will report adverse events to their respective IRB according to the local IRB's policies and procedures in reporting adverse events.

8.4 Serious Adverse Event Reporting Procedures

Serious adverse events that occur beginning with the signing of the informed consent, during treatment, or within 30 days of the last dose of treatment must be reported to the CCF Principal Investigator.

Reports of all serious adverse events (including follow-up information) will be submitted to the CCF IRB per the guidelines located in the CCF IRB Standard Operating Procedures under IRB-60 in manual. Copies of each report and documentation of IRB notification and response will be filed in the regulatory binder.

The following four types of events will be reported to the Cleveland Clinic IRB:

1. Adverse events which are serious, unexpected, and related or possibly related to participation in the research.
2. Serious adverse events that are expected in some subjects, but are determined to be occurring at a significantly higher frequency or severity than expected.
3. Other unexpected adverse events, regardless of severity, that may alter IRB analysis of the risk versus potential benefit of the research and, as a result, warrant consideration of substantive changes in the research protocol or informed consent process/document.
4. Unanticipated Problems involving risks to subjects or others or any serious or continuing noncompliance with this policy or the requirements or determinations of the IRB.

The study team will notify Biofrontera of any serious adverse events via email to [REDACTED] within 24 hours of study team awareness.

9.0 PHARMACEUTICAL INFORMATION

A list of the adverse events and potential risks associated with the commercial agents administered in this study can be found in Section 8.0.

[figure not shown]
9.1. Ameluz®: The following information about Ameluz® is cited from the package insert:

Chemical Name: 5-aminolevulinic acid (ALA)

Other Names: *delta*-aminolevulinic acid

Classification: Topical agent

Molecular Formula: The chemical name for ALA HCl is 5-amino-4-oxopentanoic acid hydrochloride (MW = 167.59). The structural formula is represented below:

Mode of Action: Photoactivation following topical application of AMELUZ occurs when aminolevulinic acid (prodrug) is metabolized to protoporphyrin IX (PpIX), a photoactive compound which accumulates in the skin. When exposed to red light of a suitable wavelength and energy, PpIX is activated resulting in an excited state of porphyrin molecules. In the presence of oxygen, reactive oxygen species are formed which causes damage to cellular components, and eventually destroys the cells. AMELUZ photodynamic therapy of AK lesions utilizes photoactivation of topically applied AMELUZ resulting from BF-RhodoLED® illumination, which provides a red light of narrow spectrum and a light dose of approximately 37 J/cm².

Metabolism: ALA is converted to PpIX within mitochondria. PpIX is then destroyed upon illumination with the incident light (see above).

Product description: AMELUZ (aminolevulinic acid hydrochloride) topical gel, 10% is a non-sterile white-to-yellowish gel. The gel formulation contains a nanoemulsion. Aminolevulinic acid, a porphyrin precursor, is a white to off-white crystalline solid. It is readily soluble in water, methanol, and dimethylformamide. Its chemical name is 5-amino-4-oxopentanoic acid hydrochloride, molecular weight is 167.59 and molecular formula is C₅H₉NO₃·HCl.

Each gram of AMELUZ contains 100 mg of aminolevulinic acid hydrochloride (equivalent to 78 mg aminolevulinic acid) as the active ingredient and the following inactive ingredients: xanthan gum, soybean phosphatidylcholine, polysorbate 80, medium-chain triglycerides, isopropyl alcohol, dibasic sodium phosphate, monobasic sodium phosphate, propylene glycol, sodium benzoate and purified water.

Product Supply: AMELUZ gel is supplied in an aluminum tube with a white, high density polyethylene (HDPE) screw cap. Each tube contains 2 g of gel.

Storage requirements and stability: AMELUZ has a shelf-life of 24 months and should be stored in a refrigerator, 2°C – 8°C (36°F – 46°F). Excursions permitted to 15°C – 30°C (59°F – 86°F).

After opening, AMELUZ can be stored for up to 12 weeks in a refrigerator at 2°C – 8°C (36°F – 46°F) if the tube is tightly closed.

Route of administration: AMELUZ® will be applied topically to the skin, as directed by the manufacturer. Specifically, using glove protected fingertips or a spatula, AMELUZ gel will be applied using sufficient amount of gel to cover the entire treatment area with 1 mm thickness, including approximately 5 mm of the surrounding skin. Application area should not exceed 20 cm² and no more than 2 grams of AMELUZ (one tube) should be used at one time. The gel can be applied to healthy skin around the lesions. Application near mucous membranes such as the eyes, nostrils, mouth, and ears (keep a distance of 1 cm from these areas) should be avoided. The study subject will be advised to avoid sunlight until he/she will return to the clinic for the illumination phase of the treatment.

Drug Procurement: AMELUZ® will be supplied by Biofrontera, in the amount of one tube of AMELUZ® gel per study patient.

Drug Accountability: The investigator or designated study personnel are responsible for maintaining accurate dispensing records of the study drug. All study drugs must be accounted for, including study drug accidentally or deliberately destroyed. Under no circumstances will the investigator allow the investigational drug to be used other than as directed by the protocol. If appropriate, drug storage, drug dispensing, and drug accountability may be delegated to the pharmacy section of the investigative site.

Drug Destruction: AMELUZ® can be stored for 12 weeks in a refrigerator at 2°C – 8°C (36°F – 46°F) if the tube is tightly closed

9.2. *Light Sources for PDT*

BF-RhodoLED® lamps are red light sources with a narrow spectrum around 635 nm that deliver a light dose of approximately 37 J/cm² within 10 minutes. PDT using AMELUZ® in combination with BF-RhodoLED® lamp is indicated for lesion-directed and field-directed treatment of actinic keratoses (AKs) of mild-to-moderate severity on the face and scalp.

10.0 CORRELATIVE / SPECIAL STUDIES:

Study patients will be identified only by patient Study ID number, and their data stored in a password-encrypted REDCap database accessible only by members of the study team.

Privacy and confidentiality: Medical information gathered in this study will be limited to what is recorded in the routine clinical PDT treatment note, along with any study-related notes entered into the electronic medical record (EPIC). Patients must consent to have photographs taken of their facial lesions at each visit, using a standard departmental photographic consent. Consent to allow use of those images in medical publications or presentations that result from the study is voluntary, as the patient will indicate in a checkbox.

11.0 STUDY PARAMETERS AND DETAILED STUDY CALENDAR

Details of 10% ALA application and red light treatment were described in detail under Section 6.0, “Treatment Plan”. The timing of visits is summarized below and in section 11.5 (“Calendar”).

11.1 **PDT treatment (Visit 1)**

All AK lesions are measured clinically and photographed. The clinician applies 10% ALA gel to entire face, without occlusion, and allows it to incubate if for either 10 min, 20 min, or 60 min, depending upon the study arm assignment. The patient will then be exposed to red light (BF-RhodoLED® device) for either 10 min or 20 min, as per the assigned study arm.

11.2 **Post-treatment assessment of side-effects (Visit 2)**

The patient will return at day 3 (± 1 day) for facial photographs to document their erythema reaction. They will also be asked about their side-effects, and insure that they know to fill out the side-effects questionnaire during the 6 days post-PDT.

11.3 **PDT treatment (Visit 3)**

This will occur 8 weeks (± 1 week) after Visit 1. All AK lesions will be measured clinically and photographed and if any remain, then the same PDT treatment regimen used at Visit 1 will be employed again here for a second round of treatment.

11.4 **Final observation (Visit 4)**

This will occur 3-6 months after Visit 1. The subject will return for final skin exam, lesion counts, and photography. A patient satisfaction questionnaire will also be administered at this visit. The large scheduling visit window is designed to maximize the likelihood of patient compliance, since many patients with AK are retirees who spend many months traveling and spend their winters in warmer climates far from Cleveland.

11.5 **Study Calendar**

CALENDAR. Timeline of procedures for patients enrolled in the study.

	VISIT 1 PDT treatment session #1	VISIT 2 Photos of skin redness	VISIT 3 PDT treatment session #2	VISIT 4 Final lesion counts
Scheduled visit: → Procedure: ↓	Day 1	Day 3 ± 1 day	Week 8 ± 1 week	Month 3-6
Sign informed consent	X			
Examine patient, mark each lesion with a pen, and count the lesions	X		X	X
Take photographs in our professional studio (frontal view and side views) to document inflammation.	X	X		
Take photographs using clinic iPhone camera to document lesion counts (pen-marks)	X		X	X

Apply topical ALA gel and incubate for 10, 20, or 60 min prior to turning on the light source (as per assigned study arms A, B, or C, respectively)	X		X	
Illuminate with red light for 20, 10, or 10 min (as per assigned study arms A, B, or C, respectively)	X		X	
Record patient-reported pain level (VAS)	X		X	
Give the patient a questionnaire to fill out at home (to describe side-effects on each of the 6 days post-PDT)	X		X	
Provide patient with a hat, sunscreen and aftercare instructions	X		X	
Patient satisfaction questionnaire				X

12.0 MEASUREMENT OF EFFECT

Endpoints to be evaluated are as follows: Pain reported by the patients during illumination will be measured on a subjective 11-point visual-analog scale (VAS). Treatment response will be evaluated by clinical exam and follow-up photographs at the two follow-up visits.

Endpoints will be:

- 12.1 Pain during illumination (VAS scale 0-10) at 1 min, 5 min, and 10 min
- 12.2 100% lesion clearance rates
- 12.3 75% lesion clearance rates
- 12.4 Visual differences observed in the before-and-after photos
- 12.5 Subject satisfaction questionnaire
- 12.6 Adverse Events- Patients' side effects log (6 days post-PDT) and Investigator assessment.

Regarding lesions clearance rates (items 12.2 and 12.3), the final efficacy outcome will be defined as the lesion counts after two treatments, and these final counts are what the estimated enrolled sample sizes are based on. Lesion status after 1 PDT treatment will also be analyzed, but not considered in the analyses of noninferiority.

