
(3) Will the new test regimen achieve reduced pain during illumination?

Answer: The likelihood is extremely high that the test regimen (or at least regimens A and B) will be nearly painless. There is now substantial evidence in the literature, showing that if visible light is delivered continuously while PpIX levels are low, then PpIX does not build up to high enough levels within pre-cancer cells to trigger pain. Instead, the PpIX is activated and destroyed as soon as it is produced. Without high PpIX concentrations in pre-cancer cells, there is no PpIX

concentration gradient and therefore no PpIX leakage from epithelial pre-cancer cells into neighboring nerve endings. The latter is the main cause of pain during traditional PDT [13].

(4) Will the new test regimen be safe?

Answer: Yes, because all test conditions (drug concentration, drug incubation time, illumination time) are either at or below the FDA-approved levels for Ameluz paired with the BF-RhodoLED® red light source.

The possible benefit of this study will be the demonstration of suggestive evidence for a new ALA-PDT regimen using Ameluz/red light for actinic keratosis, that provides a therapeutic result equivalent to current regimens, yet minimizes the pain that patients must endure.

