3.0 STUDY DESIGN

3.1 Study protocol description

The objective of this study is to test three new PDT regimens for actinic keratoses (AK) of the face that promise to greatly reduce the pain normally associated with the procedure. The new regimens, called A, B, and C, respectively, will use a photosensitizer (aminolevulinic acid, 10% ALA gel, Ameluz®) and an activating red light illumination source (BF-RhodoLED® red light panel, 635 nm) from Biofrontera, Inc. Both ALA gel and the 635 nm light source from Biofrontera are currently FDA-approved for broad-area PDT treatment of AK. The approved FDA treatment (standard regimen) specifies that ALA gel be applied topically and left on for 3 hours, followed by exposure to red light for 10 minutes. Here, the timing for topical ALA gel incubation will be shortened, to test the hypothesis that pain experienced during red light illumination can be significantly reduced while still preserving the efficacy of the procedure in terms of lesion clearance (pain and efficacy are primary endpoints). Safety and patient satisfaction will also be assessed (secondary endpoints). Timing for the 3 regimens will be as follows: **A**, ALA gel for 10 min, then red light for 20 min while ALA gel is left incubating. **B**, ALA gel for 20 min, then red light for 10 min while ALA gel is left incubating. **C**, ALA gel for 60 min, then red light for 10 min. We hypothesize that each of the new regimens will cause significantly less pain than the

current standard regimen for ALA gel/red light PDT, and that a lesion clearance response will be achieved that is similar (i.e., statistically non-inferior) to the standard treatment regimen.

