6.0 TREATMENT PLAN

6.1. Overall descriptive narrative

At the first visit (Visit #1) (Day 1), informed consent will be obtained before starting any study procedures. AK lesions will be counted by [name] and his personally-supervised CCLCM medical student researcher using clinical criteria that include presence of a visible lesion with erythema (pink or red), presence of scale, and a gritty consistency by feel (palpation). Each identified lesion will be marked with a black pen. All the marked lesions will then be counted. As a back-up, the patient's face will be photographed with all the pen-marks in place, for later independent confirmation of lesions counts.

Photographs will be taken two ways. First, documentation of the pen-marked lesions on the face will be taken using CCF i-Phones that are routinely used in our clinic; these digital photographs will be transferred and stored directly in each study patient's electronic (Epic) record.

Second, for photographic documentation of inflammation, the patient will also be photographed by a professional photographer using standardized lighting and multiple views to document the degree of inflammation at baseline.

The skin will be degreased with an alcohol wipe, lesions gently abraded with fine sandpaper, and a thin layer of ALA gel (Ameluz®) will be applied to the entire face. No occlusive dressing will be used. For patients in group **A**, the ALA gel will be left on for 10 min, and then positioned in front of the red light and exposed for 20 min; this is a (10 + 20) regimen. Patients in group **B** and group **C** will receive a (20 + 10) regimen or (60 + 10) regimen, respectively.

Pain will be assessed by asking the patient to rate their perceived pain level on an 11-point VAS scale (0= no pain, 10 = intolerable pain). Patients will be asked to report their VAS score at 1 minute after red light begins, and at the 5 minute mark (when the RhodoLED beeps). They will be asked for a final VAS score immediately after the light is turned off.

To assess side effects, patients will receive a 6-day questionnaire to record their side-effects daily during the coming week, and which asks them to confirm that they completely avoided any sun exposure during the first two days after PDT. Patients will also receive a standard set of instructions for home aftercare that includes Aquaphor emollient, a topical steroid if necessary for comfort, and instructions to wear sunscreen and avoid sunlight for 48 hr.

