8.1 Adverse Events and Potential Risks

8.1.1 *Ameluz®*

Aminolevulinic acid (ALA) is a natural component found in all cells in the human body. Ameluz is 10% ALA suspended in a lipid-based nanoemulsion. The application of ALA is not associated with any risks or side effects.

8.1.2 *Photodynamic Therapy*

When ALA is converted into PpIX in tumor cells, and illuminated with light, the following signs and symptoms are known to occur as part of the therapeutic response:

- (i) Stinging and/or burning sensation: >50%
- (ii) Erythema (localized redness): 35%
- (iii) Edema, localized: >35%
- (iv) Peeling, transient: <50%
- (v) Blister formation: rare

8.1.3 *Photodynamic Therapy response (with local cutaneous effects):*

The constellation of transient local symptoms of stinging and/or burning, itching, erythema and edema as a result of topical application of ALA followed by illumination with red light has been observed in clinical studies; for example see ref [14]. Stinging and/or burning subsides between 1 min and 24 hours after the light is turned off, and appears qualitatively similar to that perceived by

patients with erythropoietic protoporphyrin upon exposure to sunlight. There is no clear drug dose or light dose dependent change in the incidence or severity of stinging and/or burning.

8.1.4 *Extra-cutaneous adverse experiences reported:*

In previous studies, no non-cutaneous adverse events were found to be consistently associated with Ameluz application followed by red light exposure. No clinically significant patterns of clinical laboratory changes were observed for standard serum chemical or hematologic parameters in any of the controlled clinical trials.

8.1.5 *Safety in pregnancy:*

No carcinogenicity testing has been carried out using ALA. No evidence of mutagenic effects was seen in four studies conducted with ALA to evaluate this potential. No assessment of effects of ALA on fertility has been performed in laboratory animals. It is unknown what effects systemic exposure to ALA might have on fertility or reproductive function. Therefore, Ameluz is considered as Pregnancy Category C.

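### Section 12.1 lists pain at 1, 5 and 10 min without exception by arm, but Section 6.1 schedules no 10-min score in Regimen A, whose light lasts 20 min

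*Combined protocol and SAP*

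**What the plan says.** Section 3.1 states that "pain and efficacy are primary endpoints". Section 12.1 gives the pain endpoint as "Pain during illumination (VAS scale 0-10) at 1 min, 5 min, and 10 min", with no distinction between arms.

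Section 6.1 is the procedural text. Patients are asked to "report their VAS score at 1 minute after red light begins, and at the 5 minute mark", and then: "They will be asked for a final VAS score immediately after the light is turned off". The same rule is repeated there for the second treatment session at Visit 3.

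Sections 3.1 and 6.1 and the calendar in Section 11.5 agree that red light lasts 20 min in Regimen A and 10 min in Regimens B and C. The calendar marks a pain rating at Visits 1 and 3 but gives no minute marks.

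Question 1 in Section 14.1 asks whether pain is lower in each of the three regimens than in the standard 3-hour regimen. Section 14.2 takes the comparator from published results: mean 5.5 (95% CI 4.7 to 6.2) at the first session and 5.8 (4.7 to 6.9) at the second. Neither section names a minute mark, a way of combining the readings, or a primary session.

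**The concern.** The two sections agree only where light lasts 10 min. In Regimen A, staff who follow Section 6.1 take no 10-min score, and the 20-min score they do take is not a time point of the listed endpoint. A rating that was not asked for during illumination cannot be obtained later, so the mismatch has to be settled before patients are treated.

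What is at stake is a like-for-like reading of pain across the arms. If A's light-off score is put in the 10-min column, A after 20 min of light is set beside B and C after 10 min. Section 1.3 describes C as the control arm, so a reader will naturally compare A with C. With no stated summary or session, the choice among readings would also be made after the data are seen.

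**Working it through.** The plan gives no figure of its own on this point, and its sample size is driven by efficacy (Section 14.2). The check is therefore to set the listed times against the scheduled times.

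**Inputs.** Ten patients per arm (Section 4.1). Gel and light times from Sections 3.1 and 6.1. Light doses from Section 1.3: 75 J/cm² in A, 37 J/cm² in B and C.

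| Arm | Gel before light (min) | Light (min) | Times scheduled (6.1) | Times listed (12.1) | 10-min score scheduled? |
|---|---|---|---|---|---|
| A | 10 | 20 | 1, 5, 20 | 1, 5, 10 | No |
| B | 20 | 10 | 1, 5, 10 | 1, 5, 10 | Yes, as light-off |
| C | 60 | 10 | 1, 5, 10 | 1, 5, 10 | Yes, as light-off |

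**Readings not scheduled.**
- Visit 1, Regimen A: 3 × 10 = 30 listed, 10 not scheduled; 10/30 = 33%.
- Visit 1, all arms: 3 × 30 = 90 listed, 10 not scheduled; 10/90 = 11%. None is lost in B or C.
- Visit 3: up to 10 more, because the second treatment is given only if lesions remain (Sections 6.1 and 11.3). Over both sessions this is at most 20 of 180.

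**What the final scores represent.** A's final score follows 20/10 = 2 times the light duration of B and C, and 75/37 = 2.0 times the light dose.

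**Effect of using light-off in place of 10 min in A.** Write V1, V5, V10 and V20 for A's mean scores, and d = V20 − V10.
- Three-reading mean: (V1 + V5 + V20)/3 − (V1 + V5 + V10)/3 = d/3.
- Last reading alone: d.

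The documents give no value for d, so a range is shown by assumption.
- If V10 and V20 both lie within 0 to 1.09 (the interval Section 14.2 quotes for the short blue-light protocol), then |d| ≤ 1.09. The three-reading mean moves by at most 1.09/3 = 0.36 and the last reading by at most 1.09, up or down.
- If |d| were 3, the shifts would be 3/3 = 1.00 and 3.

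**Against the expected difference from the published regimen.**
- Section 14.2 means: 5.5 − 0.52 = 4.98. The first pair of shifts is 0.36/4.98 = 7% and 1.09/4.98 = 22%. The second pair is 1.00/4.98 = 20% and 3/4.98 = 60%.
- Using the value of about 1 that Section 1.2 gives for the same earlier work: 5.5 − 1 = 4.5.
- Lower published limit against upper expected limit: 4.7 − 1.09 = 3.61.

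No shift in this range cancels the expected 4.98-point difference.

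**The case against.** The strongest reply is that nothing needed for the primary pain question is missing. Question 1 compares each regimen with published mean pain and names no minute mark. Section 6.1 already provides three ratings in every arm, so the comparison can be made in A. Because the comparator is external, unequal timing between A and the other arms does not enter it. On this view the repair is one phrase in Section 12.1, replacing the 10-min mark by the end of illumination. Light-off also has some logic as an anchor: total gel contact is then 10 + 20 = 30 min in A and 20 + 10 = 30 min in B.

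Most of this stands. A reader might infer that the primary pain endpoint cannot be tested in A; the documents do not support that. A reader might also infer that the second half of A's illumination would go unscored. That follows only if staff ignore Section 6.1, and Section 11 refers to Section 6.0 for the treatment details. Section 13.1 says that a calendar and forms exist in the trial database. Those forms are not in the documents and may carry minute marks, so the counts above hold for the text alone.

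The reply does not remove the conflict. Reading 10 min as shorthand for light-off is right for B and C and wrong for A, and no section says which is meant. Rewording Section 12.1 alone would also leave no late score in A at the same light time as in B and C.

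**Conclusion.** The mismatch is real and should be fixed before treatment starts. One listed time point of a primary endpoint is not scheduled in one of three arms (33% of A's Visit 1 readings, 11% overall). A's final score is not a listed time point, and final scores follow different illumination times.

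It does not block the comparison with published pain. A reader might infer a bias against or in favour of Regimen A, or a possible reversal of the pain result. The documents establish neither size nor direction. Section 1.3 expects A and B to be nearly painless, and Section 8.1.3 says "There is no clear drug dose or light dose dependent change in the incidence or severity of stinging and/or burning". The shifts of 0.36 and 1.09 points are conditional on an interval for a mean obtained with a different drug and light, so they illustrate scale and are not limits on what A will show.

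A reader might also conclude that the mean of the three scheduled readings should be the primary score. The documents do not support fixing it. They do not say whether the published 5.5 and 5.8 were peak, final or averaged ratings, and averaging in an early 1-min score could favour the short regimens if those figures were peaks.

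**What to change.** Make Sections 6.1 and 12.1 identical, with ratings at 1, 5 and 10 min of light and at light-off in every arm, and put the same minute marks in the calendar. In B and C the 10-min and light-off ratings coincide, so only A gains a reading.

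Compare the arms at matched light times (1, 5 and 10 min). Report A's light-off score as its own end-of-illumination value, not as a substitute for its 10-min score. Matching on light time does not match gel contact, which at 10 min of light is 20, 30 and 70 min in A, B and C by design.

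Before any data are seen, state which summary of the readings and which session will be set against the published 5.5 and 5.8. Choose them from the source publication to match how those scores were taken. The statement should recognise that second-session scores come only from patients with remaining lesions.

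The cost is one verbal rating per session in A (10 at Visit 1, up to 10 more at Visit 3), one case report form line and matched wording. There are two side effects to manage. Any peak in A is taken over four readings rather than three. A plain average of all readings would give those after minute 5 a weight of 2/4 = 50% in A against 1/3 = 33% in B and C, so it should not be used to compare arms.
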